A Randomized Control Trial Treating Depression With Yoga and Coherent Breathing Versus Walking in Veterans

NCT03489122

Document Date: 3-07-2022

HUMAN SUBJECTS RESEARCH PROTOCOL

Project Title: A Randomized Controlled Trial Treating Depression with Yoga and Coherent Breathing Versus Walking in Veterans

Short Title: RCT Treating Depression with Yoga or Walking in Veterans

Protocol Version and Date: Version 5 December 31, 2021

Principal Investigator (PI): [name].

Co-Investigators: [name]., Principal Investigator for the McLean Hospital.

Institution(s): The VA Bedford Healthcare System (VABHCS) is the coordinating site. The McLean Hospital, Belmont MA will be the site for MRI imaging.

1.0 OBJECTIVE AND SPECIFIC AIMS:

Aim 1: To determine in Veterans, the effectiveness of an RCT of 12-weeks of the yoga intervention versus walking intervention, with depression and mood assessed at baseline prior to randomization, and prior to and immediately following yoga or walking interventions at weeks 4, 8, and 12, and before each scan.

Hypothesis I: In this working clinical hypothesis, subjects in the yoga group will exhibit greater improvements in depressive symptoms and mood ratings over the study compared to the walking group.

Aim 2: To measure changes in thalamic GABA levels at Scans 1, 2, and 3. (3)

Hypothesis II: In this working translational hypothesis, GABA levels will increase and depressive symptoms will decrease over the course of the 12-week intervention in the yoga group compared to the walking group.

Aim 3: To examine changes in RSA acquired at baseline prior to randomization, and prior to and immediately following yoga or walking interventions at weeks 4, 8, and 12, and before each scan.

Hypothesis III: In this working translational hypothesis, RSA levels will increase and depressive symptoms will decrease over the course of the 12-week intervention in the yoga group compared to the walking group.

Exploratory Aim: If an individual has symptoms of Post Traumatic Stress Disorder (PTSD) at screening, there will be a greater decline in PTSD symptoms with treatment in the yoga compared to the walking group. The use of the 3T scanner allows the collection of pre and post exploratory data for cortical thickness, resting state, and executive function.

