2.1.d. Trauma Response Spectrum: The Trauma Spectrum Response includes emotional dysfunction, (e.g., depression, anxiety, PTSD and anger), cognitive dysfunction, (e.g., decreased attention, concentration, memory and problem solving), somatic dysfunction, (e.g., fatigue and sleep disturbances), and alcohol and substance use disorders.(49) It is observed that disorders within the Trauma Response Spectrum are co-morbid and share fundamental imbalances – i.e., under activity in the PNS and GABA systems and over activity in the SNS. These observations support the concept that comorbid disorders observed in the Veteran population, such as MDD, PTSD and Alcohol Use Disorder (AUD) are based on the same transdiagnostic biological abnormalities. The use of an intervention that addresses abnormalities in ANS balance is novel, provides a new entry point for treatment and may enhance available treatments. In an RCT of 30 Australian Vietnam veterans, diagnosed as 100% disabled due to PTSD by the Australian VA and who had failed 30 years of treatment trials, including multiple medication combinations, a 5-day multi-component yoga and breathing intervention resulted in significant recovery from PTSD and depression at week-6 compared to the control group, and showed further improvements at 6 months.(50) On the Clinician Administered PTSD Scale, the effect size from baseline to week-6 was high at 0.90 and 2.9 at 6 months. Scores on the Center for Epidemiological Studies Depression Scale (CES-D) and Post-traumatic Stress Disorder Checklist Military (PCLM-17) also decreased significantly from baseline to week-6 and month-6. A similar study in 21 US Veterans of the wars in Iraq and Afghanistan found significant recovery in PTSD, anxiety, and physiologic measures of hyperarousal.(51) The proposed study, by monitoring PTSD symptoms in MDD subjects, will provide information on whether changes in symptoms of MDD and PTSD in response to the proposed intervention are correlated in this population, an observation that would support the transdiagnostic nature of these conditions, and the potential of an intervention that addresses a common and fundamental imbalance, having a far reaching impact on the care of Veterans.(49, 52)

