3.3.2. Study Related Procedures

3.3.2.1. Instruments: The following reliable and valid instruments will be used during the screening interview to determine eligibility, and to monitor subjects during the interventions:

- (1) Structured Clinical Interview for DSM-5 (**SCID-5**) is a widely used valid psychiatric diagnostic instrument used to screen for Axis I disorders(66);
- (2) **Columbia Suicide Safety Rating Scale (C-SSRS)** is a clinically administered instrument to assess suicide risk(67);
- (3) **Physical Activity Recall (PAR)** is a widely used structured interview that yields a weekly record of physical activity using Metabolic Equivalents (METs), a method of assessing an individual's level of physical activity in a common unit that can be calculated from a variety of activities.(55) The PAR will be obtained each week of the intervention in the event physical activity becomes a confounding factor.
- (4) **Hamilton Rating Scale for Depression (HDRS)** is a 17-item clinician administered scale frequently used to evaluate the effectiveness of antidepressants being assessed for FDA approval(68);
- (5) **Beck Depression Inventory (BDI-II)** is a 21-item self-administered instrument designed for the assessment of depressive symptoms, with higher scores reflecting greater severity(69);
- (6) **Spielberger State-Trait Anxiety Inventory (STAI)** is a self-administered instrument designed for assessment of trait anxiety (STAI-Trait) and serial assessments of state anxiety (STAI-State) with higher scores indicating higher anxiety(56);
- (7) **Clinician Administered Posttraumatic Stress Scale (CAPS)** is the gold standard clinician administered assessment for PTSD(70);
- (8) **PTSD Check List – Civilian (PCL-C)** is a 17-item self-administered scale corresponding to Diagnostic and Statistical Manual of Mental Disorders (DSM) IV criteria for PTSD. Because not all Veterans have combat experience and not all trauma is from a military experience, the civilian version of the PCL will be used. The use of the CAPS and PCL-C will allow assessment of severity of PTSD symptoms, and if present, will be modeled in statistical analyses;
- (9) **Exercise-Induced Feeling Inventory (EIFI)** is a self-administered instrument designed to assess four distinct feeling states associated with bouts of physical activity: Revitalization, Tranquility, Positive Engagement, and Physical Exhaustion.(57)

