Unless otherwise stated, instruments 4-12 are used at screening, week 4, 8, and 12. In addition, the EIFI and STAI-State are administered before and after interventions at weeks 4, 8, and 12 and before each scan. The CAPS is administered at screening and at week 12. The following instruments are given at Imaging Session 1 & 2: 2, 5, 13, and 14.

Recruitment Plan and Requirements (Table 4): Veterans will be recruited from the Bedford VA Medical Center (VABHCS) through posters, the internet, providing flyers to clinics, in meetings with staff, and recruitment at clinics affiliated with the VABHCS. Veterans who had a diagnosis of depression in the previous two years at the VABHCS will be identified via electronic health records. Targeted letters signed by the PI describing the study and inviting the Veterans to call or mail for more information will be mailed to Veterans. The mailing will include opt-in or opt-out card with postage and/or an opt-in or opt-out phone number. If a card or phone is not received within 10 days of the mailing, the identified Veterans will be called concerning their interest in the study. Data Access Request Tracker (DART) and VA Informatics and Computing Infrastructure (VINCI) will be used to identify potential subjects.

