Hypothesis 4. a. Exploratory Concurrent Antidepressants: The yoga group but not the walking group will have a decrease in depressive symptoms regardless of antidepressant treatment at the beginning of the study.

Hypothesis 4. b. Exploratory PTSD Symptoms: If PTSD symptoms are present at screening, there will be a greater decrease in PTSD symptoms in the yoga compared to the walking group as measured by CAPS and PCL-C.

Hypothesis 4. c. Resting State Connectivity will increase over the course of the study with greater increases in the yoga group.

Hypothesis 4. d. Executive Function will increase over the study as measured by the Stroop, Digit Symbol test and fMRI activation.

3.5.2. Power Analysis for Depressive symptoms and Mood Scales: Based on the power analyses below, in order to achieve adequate power for all analyses, n=70 subjects, n=35 in the yoga and n=35 in the walking intervention must complete the interventions. Using Study 4 data in subjects with MDD in the LDG, the repeated measures ANOVA for EIFI scores from screening to the completion of the intervention did not reach statistical significance in the group of n=15 (baseline: 3.1 ± 2.2 and week-12: 3.9 ± 2.7 , $F_{1,13} = 1.097$, $p = 0.31$), a post hoc power analysis was conducted, which determined that the achieved effect size was $f = .281$, with 52% power. Based on this same effect size, an a priori power calculation was conducted, which determined that **n=35** subjects would be needed to detect significant differences for BDI-II, STAI, and EIFI scores from screening to the completion of the intervention, with effect size $f = .281$, with $< = .02$ to account for multiple comparisons, and 81% power. As the power analysis for the EIFI requires the largest number of subjects (n=70), which will be used to determine sample size. In order for 70 subjects to complete the intervention, assuming a 20% drop out, 84 subjects will be randomized.

3.5.3. Power Analysis for GABA: Consistent with our analytic plan for the longitudinal questions at-hand, we can compute the statistical power for Hypothesis II an analysis sample of **n=26** subjects in each of the study groups using the mixed linear model analogue of repeated measures analysis-of-

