4.6.1.12. Psychological Risks Protection: A member of the research team will be available to answer questions concerning procedures and psychological tests at all times during the study sessions. The practice of yoga or walking interventions is unlikely to cause adverse psychological reactions. The exception is that subjects with a history of trauma may find the yoga postures elicit memories of the trauma. All subjects are screened for trauma and those with a history of PTSD or PTSD symptoms are monitored for increasing symptoms during the study. The yoga instructors will be instructed on methods for addressing the special needs of trauma victims. Subject with dissociation due to PTSD could be excluded at the discretion of the Principal Investigator. In the unlikely event that a subject has an adverse experience during an intervention session, clinical staff in addition to the yoga instructors will be available during the interventions to assess subjects who are in distress. The inclusion criteria are designed to identify subjects with MDD who are not a danger to themselves or others and who are a low risk to have an adverse reaction to the interventions. As participants are Veterans and entitle to care form the VA, if there is a risk of harm to self that would require hospitalization, they will be taken to the walk in clinic or the ER for further evaluation.

4.6.1.13. Alcohol Risk Protection: In order to prevent subjects under the influence of alcohol from participating in evaluations or the interventions, all subjects will have a Breath Alcohol Concentration (BAC) done after the written informed consent and before participation in the weeks 4, 8, and 12 evaluations and at any evaluation/intervention if research staff are concerned a participant is under the influence of alcohol. If the BAC reading is not zero, participants will not be able to participate in the evaluation/intervention. If the BAC is above 0.08% or 0.08 mcrg/l, the level of legal intoxication in Massachusetts, the participant's car keys will be taken until their BAC is less than 0.08 %. The BAC will be done with a hand held Alcosensor machine Subjects will be assessed by clinical staff for safety prior to leaving if their BAC was greater than zero. These procedures are outlined in the informed consent such that participants are aware of these procedures prior to signing the informed consent.

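### New or worsening PTSD symptoms are not compared between arms, although the protocol names yoga-elicited trauma memories as a risk and schedules PTSD scales for everyone

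*Protocol*

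**What the plan says.** **The risk.** Protocol section 4.6.1.12 regards adverse psychological reactions to either intervention as unlikely, with one exception: "subjects with a history of trauma may find the yoga postures elicit memories of the trauma". It adds that everyone is screened for trauma and that "those with a history of PTSD or PTSD symptoms are monitored for increasing symptoms during the study".

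**The data.** Section 3.3.2.1 lists the CAPS as instrument 7 and the PCL-C as instrument 8. Unless otherwise stated, "instruments 4-12 are used at screening, week 4, 8, and 12". The CAPS is such an exception: "The CAPS is administered at screening and at week 12". Neither schedule is limited to participants with PTSD symptoms.

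**The analysis.** The Exploratory Aim (section 1.0) concerns individuals with PTSD symptoms at screening, in whom "there will be a greater decline in PTSD symptoms with treatment in the yoga compared to the walking group". Hypothesis 4.b (Analysis of Hypotheses, section 3.5) repeats this for the CAPS and PCL-C: "If PTSD symptoms are present at screening, there will be a greater decrease in PTSD symptoms in the yoga compared to the walking group".

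Two other uses of the scales are stated. Section 3.3.2.1 says that using both "will allow assessment of severity of PTSD symptoms, and if present, will be modeled in statistical analyses". Section 2.1.d says that the study, "by monitoring PTSD symptoms in MDD subjects, will provide information on whether changes in symptoms of MDD and PTSD" are correlated.

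The SAP (section D.17) gives the general mixed-model approach. It mentions neither PTSD nor adverse events.

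**The concern.** The protocol attributes a specific psychological harm to the yoga postures, so its frequency could differ between arms. The scales that could show such a difference are collected in everyone. The planned comparison, however, is conditional on symptoms at screening and is framed as benefit.

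Two things are then not compared by arm: new PTSD symptoms in participants who had none at screening, and worsening in individual symptomatic participants, which an average can mask when others improve.

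At stake is what the trial can say about safety in Veterans with trauma histories. Section 2.1.c presents the proposal as addressing a lack of safety data on yoga, and section 2.2.q expects it to supply preliminary data for use in PTSD. A benefit comparison with no matching harm summary supports only part of that.

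**Working it through.** The plan gives no figure for PTSD worsening, so there is none to reproduce. The check sets the passages side by side and then sizes the gap.

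**1. Who is covered by what**

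| Participant at screening | PTSD scales scheduled | Monitoring for increase described in 4.6.1.12 | Between-arm PTSD comparison |
|---|---|---|---|
| PTSD symptoms present | Yes | Yes | Mean change only (Hypothesis 4.b) |
| PTSD history, no current symptoms | Yes | Yes | None |
| Trauma history, no PTSD history or symptoms | Yes | None described | None |

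All three rows can include people with a trauma history, the group named as at risk. The third row is missed by both the monitoring sentence and Hypothesis 4.b. The weekly adverse event sheet does not clearly fill the gap: sections 4.6.1.10 and 3.3.2.14 describe its prompts in terms of depression, self-harm and suicidality, with no PTSD prompt.

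**2. Share outside Hypothesis 4.b (illustration)**

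Inputs: in the earlier dosing study (Study 4, section 2.2.g), 8 current plus 4 sub-threshold PTSD = 12 subjects, with 32 randomised and 30 completing (section 2.2.h). The planned number of completers is 70, 35 per arm (section 3.5.2).

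- 12/32 = 37.5%, so 70 × (1 − 0.375) = 43.75, about 44 outside.
- 12/30 = 40%, so 70 × (1 − 0.40) = 42 outside, or 21 per arm.
- Assumed range: 30% symptomatic gives 70 × 0.70 = 49 outside; 70% gives 70 × 0.30 = 21 outside, about 10 or 11 per arm.

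**3. What a by-arm table could show if no events occurred**

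One-sided 95% upper limit with zero events in n: 1 − 0.05^(1/n).

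- n = 35 (all completers in an arm): 8.2%.
- n = 21 (outside Hypothesis 4.b, 40% symptomatic): 13.3%.
- n = 11 and n = 10 (outside, 70% symptomatic): 23.8% and 25.9%.

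**4. Can it be a test?**

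Chance of at least one case in an arm of 35 is 1 − (1 − p)^35. For assumed rates of 2%, 5% and 10% this is 51%, 83% and 97.5%. Power at two-sided 0.05 with 35 per arm (normal approximation for two proportions) is about 47% for 5% versus 20%, and about 80% for 5% versus 30%. The table would be descriptive.

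**The case against.** The strongest reply is that the harm is already watched for. Section 4.6.1.12 describes monitoring and has clinical staff available during sessions. Section 4.5.2.6 anticipates psychological adverse events, and an independent committee reviews adverse events (section 4.6.2.1). Exclusion 29 in section 4.4.1 removes PTSD with dissociation or flashbacks that the interventions might trigger. All of this stands. A reader might infer that new or increased symptoms would go unreported; the documents do not support that. What is missing is a definition of worsening and a comparison by arm.

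Four further points stand in whole or part:

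- **Other uses.** A reader might take Hypothesis 4.b as the only use of the PTSD scales. Sections 2.1.d and 3.3.2.1 state others, though neither yields a by-arm account of worsening.
- **Direction.** A group-by-time model estimates mean change in either direction, and no one-sided test is stated. Mean worsening among symptomatic participants would be visible; individual worsening and new onset would not.
- **Regression to the mean.** Selecting participants with symptoms might seem to favour finding a benefit of yoga. Selection precedes randomisation, so it affects both arms alike in expectation and does not favour yoga in a between-arm comparison.
- **Proxy.** An elicited memory is an episode during practice, and a PCL-C at weeks 4, 8 and 12 may miss it. That is a reason to show adverse events beside the scale, not to omit the scale.

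The SAP's silence carries little weight alone: it is one section that lists no individual hypotheses.

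**Conclusion.** The point holds as a gap in the planned analysis. A harm is named, suitable scales are scheduled for all participants, and neither document plans a between-arm summary of new or increased PTSD symptoms. The gap is clearest for trauma-exposed participants without PTSD history or symptoms at screening.

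Its size is uncertain. The estimate of 42 to 44 of 70 completers outside Hypothesis 4.b assumes that Veterans resemble the civilian subjects of the dosing study and that the undefined screening condition means current or sub-threshold PTSD. With 30% to 70% symptomatic, the number runs from 49 down to 21; if any single symptom qualified, it could be smaller still. Nor is this number a count of those at risk, because the documents give no figure for trauma history.

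The correction is worth making because it is cheap and lets the trial put a bound on a harm it names. It will not deliver a powered safety comparison.

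**What to change.** Keep Hypothesis 4.b as exploratory, but present it as a subgroup of a PCL-C mixed model (group by time) fitted in all participants.

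Add one descriptive table by arm, in all randomised participants, with:

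- the proportion whose PCL-C rises from screening by more than a margin fixed before unblinding, at weeks 4, 8 and 12, and the corresponding CAPS proportion at week 12;
- the risk difference with a 95% confidence interval;
- the same results split by PTSD symptoms at screening (present or absent), with that condition defined;
- PTSD-related adverse events alongside.

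The cost is SAP wording and one table. There are no new visits or instruments, and the sample size is unchanged. The downside is few events and wide intervals, so the table should be labelled descriptive and an absence of events should not be read as evidence of safety. Nothing in clinical management changes.

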- (10) **Pittsburgh Sleep Quality Index (PSQI)** is a self-administered instrument that assesses 9 factors of sleep over a month period, providing a composite score, with higher scores indicating poorer sleep quality.(71)
- (11) **Timeline Follow Back (TLFB)** will be used to assess alcohol consumption for three months prior to screening.(72) A format similar to the TLFB will be used for nicotine consumption.
- (12) **Brief Pain Inventory**, an eleven point Likert Scale of pain intensity will be used to assess pain over the last 24 hours.
- (13) **Stroop Color-Word Test** is a selective attention and inhibitory cognitive control task.(74)

Individual Time Line	Table 3: Individual Time Line and Collection of Dependent Variables		
	Aim 1	Aim2	Aim 3
Individual Time Line	Depression Scales	Mood Scales	GABA RSA
Telephone Screen			
Screening Session	HDRS/BDI-II 1		
3T Brain Scan			
MRS Imaging Session 1			
Pre Scan 1 Measures	HDRS/BDI-II 2	EIFI & STAI 1	RSA 1
MRS Scan 1(Baseline)			GABA 1
Randomization			
Week 4			
Pre-Week 4 Evaluation		EIFI & STAI 2	RSA 2
Week 4 Intervention			
Post-Week 4 Evaluation	HDRS/BDI-II 3	EIFI & STAI 3	RSA 3
Week 5-7 Intervention			
Week 8			
Pre-Week 8 Evaluation		EIFI & STAI 4	RSA 4
Week 8 Intervention			
Post-Week 8 Evaluation	HDRS/BDI-II 4	EIFI & STAI 5	RSA 5
Week9-11 Intervention			
Week 12			
Pre-Week 12 Evaluation		EIFI & STAI 6	RSA 6
Week 12 Intervention			
Post-Week 12 Evaluation	HDRS/BDI-II 5	EIFI & STAI 7	RSA 7
MRS Imaging Session 2			
Pre Scan 2 Evaluation	HDRS/BDI-II 6	EIFI & STAI 8	RSA 8
Scan 2			GABA 2
Interscan Intervention			
Pre-Scan 3 Evaluation		EIFI & STAI 9	RSA 9
Scan 3			GABA 3
Follow-Up 2 month	HDRS/BDI-II 6	EIFI & STAI 10	
Follow-Up 6 month	HDRS/BDI-II 6	EIFI & STAI 11	

(14) **Digit Symbol Substitution Test (DSST)** is one of the frequently used tests to measure psychomotor slowing, and is clinically sensitive because it makes demands on several processes, including perception, working memory, sustained attention and visuomotor co-ordination (Wechsler 1997).

(15) **Child Trauma Questionnaire (CTQ)** is a self-report measure of childhood trauma. (73) This scale will be given during the Week 4 evaluation at the end of the session.

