3.3.2.17. Acquisition and Analysis of GABA MRS and MRI images: Acquisition and Analysis of GABA MRS and MRI images: All MRS/MRI data will be collected on a Siemens 3T scanner at the McLean Imaging Center (MIC), McLean Hospital, Belmont, MA. High-resolution, 3D T1-weighted anatomical images will be acquired to prescribe the voxel with anatomical precision and reproducibility. Placement algorithms developed in our prior studies will be used for consistent voxel placement, based on anatomic landmarks, in the left thalamus (2x2x3 cm). A single-voxel proton MRS GABA difference-editing technique, MEscher-GArwood Point-Resolved Echo Spectroscopy Sequence – MEGAPRESS, will be used for spectral acquisition, as it permits detection of high-quality GABA spectral data. MEGAPRESS allows for collection of TE 68ms PRESS spectra for the detection of other important metabolites such as creatine, NAA, choline and glutamate. MEGAPRESS is a well-established GABA spectral difference-editing method that isolates the GABA doublet at 3.00 ppm *in vivo*. (78) When used in conjunction with PRESS (point-resolved spectroscopy). Resting state data

has been collected at pre-randomization in Study 4, and now can be collected pre and post the intervention to assess for changes in resting state over the course of the study. A resting-state fMRI scan of 8-10 minutes will complete the one-hour scanning. If time constraints require, the resting-state fMRI scan will not be done. Minor adjustments in the protocol within the safety parameters that do not change the science of the study are allowed.

As discussed with VACO, if there is a problem acquiring scans at the McLean Hospital (e.g. system upgrade) the study can proceed without the imaging component without a protocol deviation.

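### Exploratory Hypothesis 4.d predicts only a rise in executive function over time, which retest practice could produce, and it names an fMRI activation measure for which no task acquisition is described

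*Protocol*

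**What the plan says.** Protocol section 3.5.1 (Analysis of Hypotheses) gives Hypothesis 4.d as: "Executive Function will increase over the study as measured by the Stroop, Digit Symbol test and fMRI activation". No arm is mentioned. The three exploratory hypotheses before it each contrast yoga with walking. Hypothesis 4.c, for example, reads: "Resting State Connectivity will increase over the course of the study with greater increases in the yoga group".

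Section 3.3.2.1 lists the Stroop as instrument 13 and the Digit Symbol Substitution Test as instrument 14. On timing it says: "The following instruments are given at Imaging Session 1 & 2: 2, 5, 13, and 14". No alternate forms, practice run or practice adjustment are described. Neither the Stroop score to be analysed nor its direction of improvement is stated.

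On imaging, section 3.3.2.17 describes T1-weighted anatomical images, MEGAPRESS/PRESS spectroscopy of the left thalamus, and one functional run: "A resting-state fMRI scan of 8-10 minutes will complete the one-hour scanning". That run is optional: "If time constraints require, the resting-state fMRI scan will not be done". The Exploratory Aim in section 1.0 is wider: "The use of the 3T scanner allows the collection of pre and post exploratory data for cortical thickness, resting state, and executive function".

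**The concern.** There are two problems.

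First, a hypothesis that asks only for a rise between two administrations of the same test cannot separate an effect of yoga from an effect of having taken the test before. If both arms improve through familiarity, 4.d is met as written, even if neither intervention changed executive function.

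Second, 4.d relies partly on fMRI activation. An activation measure of executive function needs a task condition to contrast with something. The only functional run described is a resting-state run, which serves the connectivity hypothesis (4.c).

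What is at stake is the exploratory statement about executive function. The conclusions on depression, GABA and RSA do not depend on it.

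**Working it through.** **There is no plan figure to reproduce.** Neither document gives a sample size, power or effect size for 4.d.

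**Inputs from the documents**
- Completers: 70, of whom 56 have usable MRS data (Protocol 3.3.2.2); 35 per arm (3.5.2).
- Significance level: 0.05 (Protocol 3.5.1; SAP D.17). Sidedness is not stated there, so two-sided is assumed.
- Two administrations of each test, at Imaging Sessions 1 and 2 (3.3.2.1).

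**Assumed input.** The practice gain in units of the SD of the change score, d = (mean practice gain) / (SD of change), is set at 0.1 to 0.5. The true treatment effect is set to zero.

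**Rise-over-time reading.** For a paired t-test on n participants, the chance of a significant increase is

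1 − F(t₀.₉₇₅,ₙ₋₁), where F is the noncentral t distribution with n − 1 degrees of freedom and noncentrality d√n.

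Example: n = 70 and d = 0.3 give noncentrality 0.3 × √70 = 2.51 and a probability of 0.697.

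| d | n = 70 | n = 56 | n = 35 (one arm) |
|---|---|---|---|
| 0.1 | 0.128 | 0.110 | 0.083 |
| 0.2 | 0.378 | 0.312 | 0.209 |
| 0.3 | 0.697 | 0.597 | 0.407 |
| 0.4 | 0.910 | 0.837 | 0.633 |
| 0.5 | 0.985 | 0.957 | 0.820 |

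To convert from a gain in SDs of the score itself, the SD of change is √(2(1 − r)) for retest correlation r. A gain of 0.2 SD with r = 0.5 gives d = 0.2/1.0 = 0.2 (38% at n = 70). The same gain with r = 0.8 gives d = 0.2/0.632 = 0.316 (about 74%). The result depends heavily on both assumptions.

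**Between-arm reading.** A two-sample t-test on change scores was simulated with 20,000 replicates and the same practice gain (d = 0.3) in both arms. The rejection rate was 4.9% at 28 per arm and 5.0% at 35 per arm. Equal practice cancels.

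**The imaging measure**

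| Named in the hypothesis | Source described |
|---|---|
| 4.c resting-state connectivity | Resting-state run, optional (3.3.2.17) |
| 4.d Stroop and Digit Symbol | Instruments 13 and 14 at Imaging Sessions 1 and 2 (3.3.2.1) |
| 4.d fMRI activation | None: no task, stimulus, contrast, region or scan time |

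**The case against.** **The general model may already compare arms.** Protocol 3.5.1 and SAP D.17 plan mixed models centred on the group x time interaction, to address the aims of relative change between the two groups. The Exploratory Aim is one of those aims, and neither document prescribes a one-sample test for 4.d. This stands in part: a between-arm test is available. It does not clearly settle the matter, because the model is described for the primary effects, with data at pre-randomization and weeks 4, 8 and 12. The Stroop and Digit Symbol tests are scheduled at the imaging sessions instead, and 4.d does not ask for an arm comparison.

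**The percentages rest on assumptions.** This stands. They show what a rise-over-time test would do. A reader might infer that the plan carries a known false-positive rate, perhaps close to certainty. The documents do not support that, because they give no practice gain or retest correlation and do not prescribe that test.

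**A task run may have been intended.** A reader might infer that fMRI activation can never be produced in this trial. That goes too far. Section 1.0 lists executive function among the 3T data, separately from resting state. Section 3.3.2.1 says the Stroop "is a selective attention and inhibitory cognitive control task" and gives it at the imaging sessions without saying whether this is inside the scanner. Table 3 also has a separate 3T brain scan row with undescribed content, although it appears only once, before randomization, and so could not by itself supply a change. The allowance in 3.3.2.17 does not clearly cover an added task: "Minor adjustments in the protocol within the safety parameters that do not change the science of the study are allowed". What the text supports is that no task acquisition is described.

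**Conclusion.** The point holds as a defect of wording and specification in an exploratory hypothesis. As written, 4.d could be confirmed by retest practice common to both arms. Under assumed gains of 0.1 to 0.5 SD of change, a two-sided 0.05 test and no treatment effect, a rise-over-time test would be significant in about 13% to 98% of trials with 70 completers, or 11% to 96% with 56. The smaller number may be nearer the mark if test completion follows imaging completion. A between-arm comparison holds about 5%, provided practice is equal in the two arms.

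Separately, one of the three named measures has no described acquisition. That is an unspecified measure, not one shown to be impossible. The effect on the trial is minor.

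**What to change.** 1. Restate 4.d in the form of 4.c: the change from Imaging Session 1 to Imaging Session 2 in a named Stroop score and in the Digit Symbol score, compared between yoga and walking. State the direction of improvement for each score, and say that the group x time term is the test.
2. Remove fMRI activation from 4.d and align the Exploratory Aim in section 1.0. If a task run is in fact acquired, keep the measure and describe the task, contrast, region and scan time in 3.3.2.17.
3. Keep resting-state connectivity under 4.c only.

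The cost is protocol wording, plus the loss of one exploratory imaging claim if no task run exists. The arm comparison is also less precise than a pooled rise over time. With 35 per arm its standard error is √(1/35 + 1/35) = 0.239 SD of change, against 1/√70 = 0.120 for the pooled test. That is the price of a comparison that can be attributed to the intervention.
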